#### **3.6. Definitions related to Adverse Events (AEs)**

- *Adverse Event* means any undesirable clinical experience, including clinically significant laboratory values, occurring to the subject during the study, whether or not considered related to the investigational product or the study procedures. This includes exacerbations of pre-existing conditions.
- *Adverse Effect*: When an Adverse Event has been determined to be related to the test product or the study procedures, it is considered an Adverse Effect.
- *Exacerbations of Pre-existing Conditions* means a condition that developed before the study but which worsened or occurred with increasing frequency as study progressed.
- *“Unexpected” Adverse Events* are defined as those that would not be expected among subjects who are supplemented with the test product at safe levels.
- *Serious Adverse Event (SAE)* means any event that results in death, is immediately life threatening requires inpatient hospitalization, results in persistent or significant disability/incapacity, or is a congenital anomaly/birth defect.
- *Life-Threatening* means the subject is at immediate risk of death from the event as it occurred.

The intensity of the Adverse Event was rated as mild, moderate, or severe using the following criteria:

- Mild events require minimal or no treatment and do not interfere with the subject's daily activities.
- Moderate events result in a low level of inconvenience or concern for the therapeutic measures. Moderate events may cause some interference with functioning.
- Severe events interrupt a subject's usual daily activity and typically require systemic drug therapy or other treatment. Severe events are usually incapacitating.

If any, changes in the intensity of an AE were documented to allow an assessment of the duration of the event to be performed at each level of intensity.

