### 2.3. Study Population

The Brave study was a parallel, individually randomized controlled trial (1:1 allocation ratio) that was carried out in Jakarta, Indonesia, from 2019 to 2022 by the Department of Nutrition, Faculty of Medicine, Universitas Indonesia–[name] General Hospital and the Human Nutrition Research Center, Indonesian Medical Education and Research Institute (HNRC-IMERI), Faculty of Medicine, Universitas Indonesia. The primary objective of this study is to investigate how maternal probiotics combined with omega-3 FAs supported with government program supplements, healthy eating, and psychosocial stimulation could affect fetal brain development and later child brain functions and cognitive development at 4–6 months of age.

We screened potential participants through a patient listing from the maternal and child health unit in the local community health care and clinics. We recruited pregnant mothers in the first or second trimester of pregnancy at seven primary health centers in four municipalities in Jakarta.

Inclusion criteria of the trial:

- Indonesian pregnant women in the 2nd trimester of gestational period
- Healthy pregnancy (as measured by hemoglobin level, pregnancy status, pregnancy history)
- Having normal blood pressure
- Planning to stay in the study area until the child is 6 months old
- Willing to sign informed consent
- Having a legally acceptable representative who is capable of understanding the informed consent document and providing consent on the subject's behalf

Exclusion criteria of the trial:

- Having foreign objects in the body due to trauma, artificial heart valves, metal objects or ferromagnetic (plate, screw, clip, prosthetic), and electronic devices (pacemaker, cochlear implant, insulin pump), and being claustrophobic
- Having a history of previous gestational diabetes or having been diagnosed with gestational diabetes
- Having a history of type 1 and type 2 diabetes
- Severe anemia

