Both groups consumed the supplements from the 2nd trimester of pregnancy until 6-months postpartum, regardless of their breastfeeding status. Omega-3 FAs supplementation began at 22 weeks of pregnancy, while probiotics/placebo supplementation started at 26 weeks. The gestational age for all subjects was assessed using ultrasonography at the nearest community health center or [name] General Hospital by trained general practitioners. These start times were chosen due to the late recognition of pregnancy in our population and therefore to ensure uniform initiation for all participants. Additionally, probiotics/placebo supplementation commenced during the third trimester because of limited evidence regarding probiotics use in pregnancy before this period. The placebo probiotics capsules were indistinguishable from the active capsules in appearance, taste, and odor. Likewise, the omega-3 capsules appeared identical across groups. All mothers in both groups also received psychosocial stimulation and healthy eating modules. These modules were delivered once during pregnancy (at 30–34 weeks of gestation) and twice during postpartum (between 0–1 month and between 1–2 months after birth). In the study sample, the majority of infants were breastfed, thus likely receiving DHA via their mother's breastmilk in addition to their prenatal exposure. Outcomes assessments were performed at 36–38 weeks of gestational age for fetal brain volume and when children reached the age of 4–6 months for Bayley-III, BERA, and eye-tracking assessments. All participants, outcome assessors, and field and research teams were blinded to the allocation of the intervention.

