### **3.6.1 Reporting of Adverse Events**

All AEs reported or observed during the study were recorded in the Adverse Event Report Form/Case Report Form by the study physician (SP) from the study team and the SP from the community health center assigned to the relevant subdistrict. The need to capture this information was not dependent on whether the AE was associated with the test products or the study procedures. The SP at the community health center was responsible for determining the relationship of each AE to the test products or study procedures, assessing its intensity, and following all AEs until they are adequately resolved. Only the SP at the community health center or the referred health center was authorized to establish diagnoses and provide appropriate treatment. Any actions taken in response to an AE, along with the subsequent outcomes, were also recorded. All AEs were classified using ICD-10 codes, with preeclampsia cases recorded separately.

The Data Safety Monitoring Board (DSMB) evaluated and discussed the accumulated adverse events to monitor participant safety and provide recommendations on whether to continue, modify, or terminate the trial for certain participants. This review occurred twice for each study area (South, Central, North, and East Jakarta) during the intervention period. If necessary, in the worst-case scenario, the DSMB could decide to stop the trial. An SP coordinator from the study team was assigned to ensure all of these procedures were carried out appropriately.

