## **6. SAFETY OUTCOMES**

AEs and SAEs, including participant deaths and hospitalizations, were monitored by study site physicians and reported to the DSMB in accordance with the DSMB protocol. Safety analyses will be conducted in the safety analysis set, defined as all participants who received at least one dose of the study treatment. Safety data, including laboratory parameters, will be summarized descriptively by treatment group, reporting the number and percentage of participants experiencing each AE or SAE.

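### The SAE definition omits prolongation of an existing hospital stay, so some complications around delivery may be tabulated as AEs rather than SAEs

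*SAP*

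**What the plan says.** Section 3.6 defines an SAE as an event that causes death, or that "is immediately life threatening requires inpatient hospitalization, results in persistent or significant disability/incapacity, or is a congenital anomaly/birth defect". Life-threatening has its own entry in the same section: it "means the subject is at immediate risk of death from the event as it occurred". I therefore read life-threatening and hospitalization as two separate criteria, although nothing separates them in the text. That makes five criteria in all.

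Section 2.4 has both groups taking supplements from the second trimester "until 6-months postpartum, regardless of their breastfeeding status", so every birth falls inside the safety period.

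Section 3.6.1 describes capture: "All AEs reported or observed during the study were recorded in the Adverse Event Report Form/Case Report Form". It adds that "All AEs were classified using ICD-10 codes, with preeclampsia cases recorded separately", and that "Any actions taken in response to an AE, along with the subsequent outcomes, were also recorded".

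Section 3.6.2 sends SAEs and unexpected AEs to the DSMB by the same 24-hour route.

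Section 6 says that "AEs and SAEs, including participant deaths and hospitalizations" were monitored. It plans a descriptive table by group of the number and percentage of participants with each AE or SAE, among those who took at least one dose.

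**The concern.** The usual ground for calling a non-fatal event serious is that it puts the patient in hospital. For someone already in hospital, the counterpart is that it keeps her there longer. Section 3.6 has the first and lacks the second. Read plainly, a complication that arises after a woman has been admitted to give birth, and that costs her several more days in hospital, does not require hospitalization because she is already an inpatient. Unless it meets another criterion it is an AE only.

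This gap matters more here than in most trials because delivery lies within follow-up for every participant. Safety is a stated aim of the trial (section 2, Study Synopsis), and the SAE rows of the section 6 table depend directly on this definition. SAEs are usually few, so moving a handful of events between categories can change how the table reads.

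**Working it through.** No arithmetic in the plan can be reproduced: the SAP gives no SAE rate, no expected event count and no length-of-stay figure. The check is a reading of the definition against the other safety sections.

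1. **Is the definition complete as written?** Yes. It states what an SAE means and lists five criteria: death, immediate threat to life, inpatient hospitalization, persistent or significant disability, congenital anomaly. There is no residual criterion for other medically important events. Because the SAP chose to define the term, this is not a point merely left to the protocol.

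2. **Does another section supply the missing criterion?** No. Sections 3.6.1, 3.6.2, 3.8 and 6 use the terms AE and SAE without adding to the definition. Section 6 names deaths and hospitalizations but not prolonged stays.

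3. **Can the gap come into play?** Only if participants were inpatients when an event arose. Section 2.4 puts delivery inside the observation period. The SAP does not say where women delivered. The nearest statement is that they were recruited "at seven primary health centers in four municipalities in Jakarta", which concerns recruitment. Inpatient status at birth is plausible but is an assumption.

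4. **Which events are affected?** Only those whose sole serious feature is a longer stay:
   - fatal, life-threatening or disabling events and birth defects are SAEs under section 3.6 wherever they occur;
   - an event causing a new admission or a readmission is an SAE;
   - an event that only lengthens a current stay is, on the plain reading, an AE.

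5. **What happens to an affected event?** It is still recorded and coded (section 3.6.1) and still tabulated by arm (section 6). If judged unexpected, it also goes to the DSMB by the SAE route (section 3.6.2). It carries the wrong seriousness label but is not lost.

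6. **Scale.** With 157 women per arm (section 2.4), one per cent is 0.01 × 157 = 1.57 women per arm, or 0.01 × 314 = 3.14 in the trial. For an assumed share of 1% to 10% with an event serious only by prolongation, that gives 1.57 to 15.7, about 2 to 16 women per arm. The share has no source in the SAP, so this range only shows scale and is not an estimate.

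**The case against.** The strongest case on the other side has four parts.

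- **The hospitalization criterion can be read more widely.** A study physician could take it to cover any event that itself needs inpatient care, including in a woman already admitted. The SAP does not show how it was applied. This stands, and it is why the conclusion is that events may be misclassified. It also shows that the wording leaves the matter to each assessor.

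- **No harm is hidden.** A reader might infer that the safety report misses delivery complications. The documents do not support that: all AEs are recorded and tabulated, and preeclampsia is recorded separately. This stands in full.

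- **Routine births do not inflate the count.** A reader might also infer from section 6 that normal delivery admissions could swamp the SAE table. Section 3.6 requires an AE to be an undesirable clinical experience, and section 3.6.2 applies the seriousness criteria to adverse events. An uncomplicated delivery is not one. The mention of hospitalizations in section 6 describes what was monitored and does not make every admission an SAE. An explicit sentence would help, but only as clarification.

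- **The consequence is limited.** Safety is summarized descriptively, no efficacy result depends on it, and section 2.5 has field and research staff blinded, so no difference in misclassification between arms is shown. This stands. It limits the weight of the point without removing it, since the SAE counts are themselves a planned result.

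Newborns need a separate caution. The safety set is participants who took a dose, and infants are not dosed directly. Whether newborn events enter the SAE table is unclear, so I attach no size to them.

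**Conclusion.** The point holds in a limited form. The section 3.6 definition covers events that require inpatient hospitalization and omits events that prolong it, and nothing elsewhere in the SAP fills the gap. If women were inpatients at birth, and if assessors read the criterion as meaning a new admission, complications that only lengthened the stay are labelled AEs and not SAEs in the section 6 table. Both conditions are assumptions.

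The direction, if there is an effect, is towards too few SAEs. Its size cannot be derived from the SAP. A reader might go further and conclude that peripartum harm is understated overall or that the comparison between arms is biased. Neither is supported: the events stay in the AE table, and nothing suggests that the arms were classified differently. It is still worth correcting, because the seriousness rule as stated can misplace events in a planned safety table and the remedy is cheap.

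**What to change.** For the section 6 analysis:

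1. Add prolongation of an existing hospitalization to the seriousness criteria in section 3.6, and separate the life-threatening and hospitalization criteria in the wording.
2. State how events that lengthened a stay were classified during the trial.
3. Have recorded AEs reviewed against the amended criterion, blind to arm, using the actions and outcomes already on the AE forms.
4. Report SAE counts by arm under the definition as it now stands and under the amended one, and state how many events could not be reclassified.
5. As a clarification only, note that admission for an uncomplicated delivery is not an AE.

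New wording alone would recover nothing: the trial ran from 2019 to 2022 and the SAP is dated August 2025, so the review of existing forms is the part that matters. No new data collection and no change to the efficacy analyses is needed. The cost is some review time and slightly higher SAE counts. The main risk is that the forms may hold too little on length of stay, since section 3.6.1 mentions actions and outcomes but not duration of admission. That is why the number of unclassifiable events should be reported.

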### **3.6.1 Reporting of Adverse Events**

All AEs reported or observed during the study were recorded in the Adverse Event Report Form/Case Report Form by the study physician (SP) from the study team and the SP from the community health center assigned to the relevant subdistrict. The need to capture this information was not dependent on whether the AE was associated with the test products or the study procedures. The SP at the community health center was responsible for determining the relationship of each AE to the test products or study procedures, assessing its intensity, and following all AEs until they are adequately resolved. Only the SP at the community health center or the referred health center was authorized to establish diagnoses and provide appropriate treatment. Any actions taken in response to an AE, along with the subsequent outcomes, were also recorded. All AEs were classified using ICD-10 codes, with preeclampsia cases recorded separately.

The Data Safety Monitoring Board (DSMB) evaluated and discussed the accumulated adverse events to monitor participant safety and provide recommendations on whether to continue, modify, or terminate the trial for certain participants. This review occurred twice for each study area (South, Central, North, and East Jakarta) during the intervention period. If necessary, in the worst-case scenario, the DSMB could decide to stop the trial. An SP coordinator from the study team was assigned to ensure all of these procedures were carried out appropriately.

### **3.6.2 Reporting of Serious or Unexpected Adverse Events**

If, according to the review of the study physician, an adverse event met the criteria of a SAE or an unexpected adverse event, the following procedure was followed:

- The Principal Investigator reported the SAE or unexpected AE with the potential causality towards participation in the study, immediately (and in all cases within 24 hours) of becoming aware of the event to the DSMB.
- The Principal Investigator provided the minimal information i.e. date of birth, subject's number, date of SAE or unexpected AE, serious adverse event term and causality, immediate follow up.
- The DSMB had to file a report, including the duration and actions taken, and provided advice whether or not the event is considered attributable to the test product or the study procedures and whether the study should be continued or modified. This report was delivered to the Principal Investigator as soon as possible to take further action. The Principal Investigator informed the Ethical Committee of the Faculty of Medicine, Universitas Indonesia, and [name] National Hospital within three calendar days.

- The PI will inform the grantor of the project and providers of intervention about the SAE or unexpected AE, action taken, and recommendation of DSMB.
- The subject who experienced SAE or unexpected AE was followed and treated clinically and by laboratory studies until all parameters had returned to normal or have resolved.

### **3.7. Adjustment for Multiplicity**

No adjustment for multiple comparisons will be performed.

### **3.8. Interim Analyses**

We assessed blinded data every week to review and resolve errors. We monitored adherence to supplementation throughout the trial and responded to any issues that resulted in low adherence.

DSMB monitored data for evidence of any AEs, SAEs, or deaths related to the allocation, and provided recommendations if need to stop the trial prematurely based on predefined protocol. Every SAE was reported to the DSMB within 24 hours to provide recommendation of continuation, modification, or termination. AEs and SAEs were monitored daily by study site physician team, and a summary report were shared monthly to the DSMB. The DSMB met twice for each municipality (South, Central, North, and East Jakarta) throughout the study to review the compiled data. No interim analyses were planned for this study.

### **3.9. Handling of Missing Data**

We will handle missing data first by tabulating the proportion of subjects lost to follow-up by allocation groups and examining if missingness differs significantly (e.g., >10% absolute difference) by allocation groups or key baseline characteristics. Additionally, baseline characteristics of participants with available outcome data will be compared to those with missing outcome data. To further assess potential bias introduced by missingness, we will evaluate balance in baseline covariates between allocation groups, both in the original trial sample and the sample retained at follow-up. Efficacy analyses and other exploratory analyses will be performed in the full analysis set (i.e., all subjects randomly assigned to the study, including those who did not receive a dose of study treatment).

### **3.10. Definitions Related to Estimands**

We will use treatment policy estimand with an intention-to-treat analysis for all primary and secondary objectives. The treatment policy estimand evaluates the treatment effect on the variable regardless of the intercurrent event. In other words, the outcome of interest is considered whether or not an intercurrent event occurred before its measurement, e.g. the final outcome is of interest irrespective of whether the participant takes additional medication or has low compliance.

## 4. DESCRIPTIVE STATISTICS

### 4.1. Recruitment and Follow-up

The status of participants will be reported using a CONSORT flowchart. Caregivers were informed that the children could withdraw from the study at any time. A senior staff person visited caregivers who indicated that the children wanted to withdraw to discuss the family's concerns and reasons for withdrawal. Children who had already withdrawn their participation were not followed up on unless they requested to rejoin the trial. All procedures related to recruitment, follow-up, and withdrawal were conducted in accordance with the trial's ethical approvals.

### 4.2. Baseline Characteristics

We will present characteristics of the study sample with continuous data as mean and SD or as median with 25th and 75th percentiles. Categorical variables will be presented as frequencies and percentages. We will indicate sample sizes for variables with more than 20% missing observations in the footnotes. Variables of the baseline characteristics are listed in **Table 1**, which best describe the study population, particularly in relation to child nutrition and cognition, as our predictor and outcome of interest in this analysis.

**Table 1.** Characteristics of the study sample

Variable	Definition
Baseline	
Child sex	2 categories: Female or male
Birth order	2 categories: First born or $\geq$ second-born
Municipality economic status	2 categories: High (Central and South Jakarta) or low (North and East Jakarta)
Maternal height	Maternal height in centimeters
Maternal pre-pregnancy BMI	BMI in kg/m 
Maternal hemoglobin level at baseline	Hemoglobin level in g/L
Maternal history of hypertension	2 categories: With a history of hypertension or without any history of hypertension
Maternal age	Maternal age in years
Maternal education	3 categories: No education/incomplete primary/unknown, Completed primary, Completed secondary or greater
Number of children	Number of children under 5 years old in the household
Number of household members	Total number of people in the household
Maternal marital status	3 categories: Monogamous marriage, polygamous marriage, or unmarried [single, divorced, widowed]
Maternal occupation	2 categories: Housewife or working mother
Paternal occupation	2 categories: Non-private sector and unemployed, or private sector
Monthly household expenditure	Household expenditure in Indonesian Rupiah per month
Endline	
Child age at outcome assessment	Child age in months (or gestational week for fetal brain outcome)
HOME inventory	HOME inventory score at the age of 4–6 months

Screen time	Screen time per day in minutes at the age of 4–6 months
-------------	---

HOME inventory, the Home Observation for Measurement of the Environment inventory.

